7.5.1 Cytochrome P450 and antileukemic drugs

Since concurrent use of enzyme inducing anticonvulsants (e.g., phenytoin, phenobarbital, and carbamazepine) with anti-leukemic therapy has recently been associated with inferior EFS, every effort should be made to avoid these agents, as well as rifampin, which also induces many drug metabolizing enzymes.²⁴ Neither gabapentin nor levetiracetam induce hepatic drug metabolizing enzymes

and may be suitable alternative anticonvulsants. Azole antifungals (listed in the table below) and the macrolide group of antibiotics (listed in the table below) may have potent inhibitory effects on drug-metabolizing enzymes. Patients receiving some anti-leukemic drugs (e.g., vincristine, anthracyclines, etoposide) may experience excess toxicity when these agents are given concomitantly; alternate antifungal and antibacterial therapy should be used where possible (see table below).

DRUGS	POTENTIAL INTERACTION	ACTION TO BE TAKEN
Anticonvulsants	Induction of drug metabolizing enzymes Lowered EFS	AVOID phenytoin, phenobarbital, carbamazepine Consider gabapentin or levetiracetam as alternative
Rifampin	Induction of drug metabolizing enzymes	DO NOT USE
Azole Antifungals (itraconazole*, posaconazole, voriconazole, ketoconazole, isavuconazole)	Inhibition of drug metabolizing enzymes	CONSIDER ALTERNATIVE MEDICATIONS May need dose reductions of vincristine*, anthracyclines, etoposide, steroids
Macrolide Antibiotics (erythromycin, clarithromycin, azithromycin, roxithromycin, telithromycin)	Inhibition of drug metabolizing enzymes	CONSIDER ALTERNATIVE MEDICATIONS May need dose reductions of vincristine, anthracyclines, etoposide, steroids

* Itraconazole should NOT be used in patients who are receiving vincristine due to a serious drug-drug interaction leading to severe neurotoxicity.^{32,33}

This is not an inclusive list. Because the lists of these agents are constantly changing, it is important to regularly consult frequently updated medical references.

7.5.2 CYP3A4 Interactions and palbociclib

In vitro data indicate that CYP3A and sulfotransferase (SULT) enzyme SULT2A1 are mainly involved in the metabolism of palbociclib. Palbociclib is a strong substrate of CYP3A4 isozyme.

The concomitant use of strong CYP3A4 inhibitors including, but not limited to atazanavir, boceprevir, clarithromycin, itraconazole, ketoconazole, lopinavir/ritonavir, nefazodone, nelfinavir, posaconazole, saquinavir, ritonavir, telaprevir, telithromycin, voriconazole, and grapefruit or grapefruit juice, may increase palbociclib plasma concentrations and should be avoided (see [Appendix III](#) for list of agents).

The concomitant use of strong CYP3A4 inducers including, but not limited to carbamazepine, enzalutamide, felbamate, nevirapine, phenobarbital, phenytoin, primidone, rifabutin, rifampin, rifapentin, and St. John's wort, may decrease palbociclib plasma concentrations and should be avoided (see [Appendix III](#) for list of agents).

Strong inducers and/or strong inhibitors of CYP3A4 are prohibited from 14 days prior to enrollment to the end of the study. See Appendix III for a list of agents.

The use of moderate inhibitors and/or inducers of CYP3A4 should be avoided as well for the duration of the study, if reasonable alternatives exist.

Palbociclib is a weak time-dependent inhibitor of CYP3A4 in humans. The use of sensitive CYP3A4 substrates and CYP3A4 substrates with a narrow therapeutic range should be avoided for the duration of the study if reasonable alternatives exist ([Appendix III](#)).

8.0 EVALUATIONS/MATERIAL AND DATA TO BE ACCESSIONED

8.1 Required Clinical, Laboratory and Disease Evaluation

All clinical and laboratory studies to determine eligibility must be performed within 7 days prior to enrollment unless otherwise indicated. Laboratory values used to assess eligibility (see [Section 4.0](#)) must be no older than seven (7) days at the start of therapy. Laboratory tests need **not** be repeated if therapy starts **within** seven (7) days of obtaining labs to assess eligibility. If a post-enrollment lab value is outside the limits of eligibility, or laboratory values are older than 7 days, then the following laboratory evaluations must be re-checked within 48 hours prior to initiating therapy: bilirubin, ALT (SGPT) and serum creatinine. If the recheck is outside the limits of eligibility, the patient may not receive protocol therapy and will be considered off protocol therapy. Imaging studies, bone marrow aspirate and/or biopsy, must be obtained within 14 days prior to start of protocol therapy (repeat the tumor imaging if necessary).

STUDIES TO BE OBTAINED	Pre-Study	During Cycle 1	End of Protocol Therapy- Day 32[^]
History	X	Weekly	
Physical exam with vital signs	X	Weekly	X
Height, weight, BSA	X		X
Performance status	X		X
Pregnancy test ¹	X		
CBC, differential, platelets	X	Twice Weekly (every 3 to 4 days) ³	X
CSF cell count & cytospin	X*	With each IT	
Pharmacokinetics ²	X	X	
Urinalysis	X		
Electrolytes including Ca ⁺⁺	X	Weekly	X
Creatinine, ALT, bilirubin	X	Weekly	X
Direct Bilirubin	X ¹²		
Albumin	X		
ECHO or gated radionuclide study	X		X
12-lead EKG	X		X
Chest x-ray	X		
Patient Diary ¹¹		Weekly	X
ADDITIONAL STUDIES: ALL ONLY			
Bone marrow aspirate for morphology and MRD	X		X ⁴
Absolute Blast Count (ABC)		Day 4 ⁵	
Correlative biology studies ⁶	X	Day 4	X
ADDITIONAL STUDIES: LL ONLY			
Chest ⁷ and neck CT	X		X ^{7,8}
Abdomen/Pelvis CT or MRI	X		X ⁸
Chest x-ray	X		
PET scan (recommended)	X		X
Bone scan ⁹	X ⁹		X ⁹
Bilateral bone marrow aspirates and biopsies for morphology	X		Only if positive at diagnosis ¹⁰

- [^] Abnormal laboratory tests must be re-checked by Day 42 since some toxicities require resolutions to \leq Grade 2 or baseline by Day 42 (see DLT criteria).
- * May be done with the Day 1 lumbar puncture with IT therapy.
- ¹ Women of childbearing potential require a negative pregnancy test prior to starting treatment; sexually active patients must use an acceptable method of birth control. Abstinence is an acceptable method of birth control.
- ² See [Section 8.2](#) for timing of PK studies.
- ³ If patients have Grade 4 neutropenia then CBCs should be checked at least every other day until recovery to Grade 3.
- ⁴ Bone marrow aspirate must be obtained on Day 32 ± 2 days. MRD should be obtained with this end of cycle bone marrow if patient $< 5\%$ blasts by morphology. If peripheral blood count recovery is delayed at the end of the cycle, repeat a bone marrow aspirate just prior to or on Day 42 regardless of counts. If still delayed repeat a bone marrow every 7-14 days after Day 42 until count recovery or relapse.
- ⁵ Absolute blast count should be performed on Day 4 prior to administration of chemotherapy.
- ⁶ See [Section 8.3](#) for timing of Correlative Biology studies (optional). Peripheral blood samples should be collected PRIOR to administration of Day 4 chemotherapy, if absolute blast count is $>1000/\text{mm}^3$.
- ⁷ Obtain chest CT for all LL patients at baseline and on Day 32. The baseline chest CT may be delayed until the patient is stable. A PET-CT can be used instead of a CT (See [Section 12.4](#)).
- ⁸ If imaging studies are negative at baseline, no further imaging is needed on Day 32. A PET-CT can be used instead of a CT (See [Section 12.4](#)).
- ⁹ Bone scan as clinically indicated; perform at Day 32 only if patient has disease at baseline. May substitute a PET scan for a bone scan, however, a bone scan is preferred for bone symptoms.
- ¹⁰ LL should have bone marrow aspirates and biopsies on Day 32 ± 2 days if $\geq 5\%$ marrow involvement was present at diagnosis
- ¹¹ Patient diary (see [Appendix XII](#)) should be reviewed after completion of each treatment cycle and uploaded into RAVE. The patient diary should be collected and reviewed weekly during Cycle 1.
- ¹² Collect direct bilirubin before start of protocol therapy and as clinically indicated.

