5.4.1 Non-hematological dose-limiting toxicity attributable to palbociclib

5.4.1.1 Any Grade 3 or greater non-hematological toxicity possibly, probably or definitely attributable to palbociclib with the specific **exclusion** of:

- Grade 3 nausea, anorexia, fatigue, malaise, weight loss, vomiting or diarrhea that returns to \leq Grade 2 or baseline within 3 days with supportive care
- Grade 3 or 4 liver enzyme elevation, including ALT/AST/GGT, that returns to Grade \leq 2 within 42 days of the start of therapy. Note: For the purposes of this study the ULN for ALT is defined as 45 U/L. Adverse event grades will be based on increases above the upper limit of normal, regardless of the subject's baseline. See [Appendix XI](#) for toxicity grading table
- Grade 3 direct bilirubin elevation that is asymptomatic and returns to \leq Grade 1 within 42 days of the start of therapy
- Grade 3 total bilirubin elevation that resolves to \leq Grade 1 within 42 days of the start of therapy
- Grade 3 or 4 fever, febrile neutropenia or infections with or without hospitalization
- Grade 3 or 4 hypotension explained by sepsis
- Grade 3 or 4 isolated electrolyte abnormalities that resolve, with or without intervention, to \leq Grade 2 within 3 days. Electrolyte supplementation is encouraged.
- Grade 3 tumor lysis syndrome that resolves to \leq Grade 2 within 3 days
- Grade 3 mucositis that resolves to \leq Grade 2 within 3 days
- Grade 3 epistaxis
- Grade 3 bone and/or pain in extremity
- If a patient requires more than 4 doses of palbociclib to be held due to toxicity this is a DLT.

5.4.1.2 Any Grade 2 non-hematological toxicity that persists for \geq 7 days and is considered sufficiently medically significant or sufficiently intolerable by patients that it requires treatment interruption.

5.4.1.3 Note: Allergic reactions that necessitate discontinuation of study drug will not be considered a dose-limiting toxicity.

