All baseline studies must be performed prior to starting protocol therapy unless otherwise indicated below. For information related to prestudy observations please refer to [Section 8.0](#)

- a. History
- b. Physical exam with vital signs
- c. Height, weight, BSA
- d. Performance status
- e. Pregnancy test: Women of childbearing potential require a negative pregnancy test prior to starting treatment; sexually active patients must use an acceptable method of birth control. Abstinence is an acceptable methods of birth control. All women of childbearing potential must have a pregnancy test done every cycle prior to initiation of a new cycle.
- f. CBC, differential, platelets: Twice weekly during Cycle 1. If patients have Grade 4 neutropenia or thrombocytopenia, CBCs should be checked at least every other day until recovery to Grade 3 or until the criteria for dose limiting toxicity are met.
- g. Urinalysis
- h. Electrolytes including Ca⁺⁺
- i. Pharmacokinetics (required): See [Section 8.2](#) for details.
- j. Creatinine, ALT, bilirubin
- k. Albumin
- l. ECHO or gated radionuclide study
- m. 12-lead EKG
- n. Patient Diary
- o. Bone Marrow Aspirate for morphology and MRD. Must be performed on Day 32 ± 2 days.
- p. Absolute Blast Count; Absolute blast count should be performed on Day 4 prior to administration of chemotherapy.
- q. Correlative Biology Studies See Section 8.3 for details.

This listing only includes evaluations necessary to answer the primary and secondary aims. OBTAIN OTHER STUDIES AS REQUIRED FOR GOOD CLINICAL CARE.

Comments

(Include any held doses, or dose modifications)

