APPENDIX XI: TOXICITY-SPECIFIC GRADING

Total Bilirubin

Grade 1:	> ULN- ≤ 1.5 x ULN
Grade 2:	> 1.5 x ULN - 3.0 x ULN
Grade 3:	> 3.0 x ULN -10.0 x ULN
Grade 4:	> 10.0 x ULN

Direct Bilirubin Increase*

Grade 1:	< 3.0 mg/dl
Grade 2:	3.1 mg/dl - 5.0 mg/dl
Grade 3:	5.1 mg/dl-6.0 mg/dl
Grade 4:	≥ 6.1 mg/dl

*To be reported under the SOC of ‘Investigations –Other, specify’ as ‘Direct Bilirubin Increased’

ALT: For the purpose of this study, the ULN for SGPT is 45 U/L regardless of baseline.

Grade 1:	> 45 U/L - ≤ 135 U/L
Grade 2:	136 U/L - 225 U/L
Grade 3:	226 U/L - 900 U/L
Grade 4:	> 900 U/L

AST: For the purpose of this study, the ULN for SGOT is 50 U/L regardless of baseline.

Grade 1:	> 50 U/L - ≤ 150 U/L
Grade 2:	151 U/L -250 U/L
Grade 3:	251 U/L -1000 U/L
Grade 4:	> 1000 U/L

GGT:

Grade 1:	> ULN- 2.5 x ULN
Grade 2:	> 2.5 x ULN - 5.0 x ULN
Grade 3:	> 5.0 x ULN -20.0 x ULN
Grade 4:	> 20.0 x ULN

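### AST or GGT alone can make a patient a DLT under Section 5.4.1.1, but ALT is the only liver enzyme the schedule requires, so such a DLT is found only where a site chooses to draw them

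*Combined protocol and SAP*

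**What the plan says.** **DLT rule (5.4.1.1).** The base rule counts "Any Grade 3 or greater non-hematological toxicity possibly, probably or definitely attributable to palbociclib". The list of exclusions then takes out "Grade 3 or 4 liver enzyme elevation, including ALT/AST/GGT, that returns to Grade" 2 or lower within 42 days of the start of therapy. An attributable Grade 3-4 AST or GGT rise that does not come down in that time falls outside the exclusion and is a DLT by itself.

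**Grading (Appendix XI).** Both enzymes have grade limits. For AST: "AST: For the purpose of this study, the ULN for SGOT is 50 U/L regardless of baseline", with Grade 3 starting at 251 U/L. For GGT, Grade 3 is "> 5.0 x ULN -20.0 x ULN".

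**Required tests (8.1, Appendices VI and VII).** The 8.1 table has one row with a liver enzyme, "Creatinine, ALT, bilirubin", marked pre-study, weekly and Day 32. The maps repeat it as "j. Creatinine, ALT, bilirubin", against Days 4, 11, 18, 25 and 32. The pre-treatment recheck covers "bilirubin, ALT (SGPT) and serum creatinine". The maps describe their contents this way: "This listing only includes evaluations necessary to answer the primary and secondary aims". The first primary aim is the MTD/RP2D.

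**Decision rule (11.3, 11.2.2).** Two or more DLTs among up to six patients mean that the MTD has been exceeded, with a narrow exception for expanding the cohort. DLTs in the expansion phase count toward the same one-third limit.

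**The concern.** The DLT definition reaches two enzymes that the schedule never asks anyone to measure. Whether a patient with an isolated, persistent AST or GGT rise is a DLT then depends on the local chemistry panel and not on the protocol. The error has one direction: an unmeasured enzyme cannot add a DLT, only hide one.

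In a cohort of six, one event can decide the outcome. Two DLTs in six exceed the MTD; one in six does not.

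The missing baseline matters as well. Eligibility (4.1.6.2) limits ALT but not AST or GGT. Where one of them is first drawn during treatment and found high, there may be no pre-treatment value to help judge attribution to palbociclib.

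**Working it through.** **Step 1: the DLT rule against the required tests.** The plan states no figure to reproduce here, so the first check sets the sections side by side.

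| Place | ALT | AST | GGT |
|---|---|---|---|
| 5.4.1.1, liver-enzyme clause | named | named | named |
| Appendix XI, grades | yes | yes | yes |
| 8.1 table | required | absent | absent |
| Appendix VI (ALL), item j | required | absent | absent |
| Appendix VII (LL), item j | required | absent | absent |
| 4.0 and 8.1, pre-treatment recheck | yes | absent | absent |

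Across the six scheduled chemistry points (pre-study and Days 4, 11, 18, 25 and 32), AST and GGT are required at none.

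**Step 2: does another provision close the gap?**
- The Day 42 footnote in 8.1 requires a recheck of tests already abnormal. It secures follow-up of a known AST or GGT abnormality but does not produce a first measurement.
- The maps ask for other studies as good care requires. That leaves the choice to the site.
- Section 11.2.1 makes DLT evaluability depend on appropriate toxicity monitoring but names no test. A patient with no AST or GGT value can count as evaluable and free of DLT.

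None of the three requires a first draw.

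**Step 3: effect on the decision.** The documents give no rate for AST- or GGT-only DLTs, so every rate below is an assumption. Let *a* be the DLT probability from all other causes and *m* the added probability of a DLT shown by AST or GGT alone. For six patients:

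P(2 or more of 6) = 1 − (1−p)^6 − 6p(1−p)^5

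Use p = a if no site draws the enzymes, and p = a + m if every such DLT is found.

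For example, with a = 0.10 and m = 0.02:
- p = 0.10: 1 − 0.5314 − 0.3543 = 0.114
- p = 0.12: 1 − 0.4644 − 0.3800 = 0.156
- Difference: 0.041

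| a | None found | All found, m = 0.02 | Shortfall | All found, m = 0.05 | Shortfall |
|---|---|---|---|---|---|
| 0.10 | 0.114 | 0.156 | 0.041 | 0.224 | 0.109 |
| 0.15 | 0.224 | 0.271 | 0.048 | 0.345 | 0.121 |
| 0.20 | 0.345 | 0.394 | 0.049 | 0.466 | 0.121 |
| 0.25 | 0.466 | 0.513 | 0.047 | 0.580 | 0.114 |

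The shortfall runs from about 4 to 12 percentage points. This is the worst case, with no site testing. If half of these DLTs were found through local testing (p = a + m/2), the shortfall would be about half as large, roughly 2 to 6 points.

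**The case against.** **AST and GGT are named only inside an exclusion.** The base rule is broad and already reaches other analytes that 8.1 does not schedule, such as glucose or amylase and lipase. On this view the clause only keeps reversible rises from counting, and Appendix XI only grades a value if one exists. The reading is fair as far as it goes: neither passage orders screening. But the protocol names these two enzymes in the DLT text and grades them in Appendix XI, so leaving their measurement to chance is harder to defend than for an analyte it never mentions in that text.

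**The event is narrow.** This stands, and it limits the size of the point.
- It needs AST above 250 U/L or GGT above 5 times ULN.
- It needs attribution to palbociclib although the backbone affects the liver: doxorubicin hepatotoxicity (9.5.2) and pegaspargase liver-test abnormalities (9.8.2) are each listed at 5-20%.
- It must persist to Day 42, which is 42 − 21 = 21 days after the last scheduled palbociclib dose.
- ALT and bilirubin, both drawn weekly, must not already have made the patient a DLT.

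**The CAEPR gives uneven support (9.1.10).** AST increase is a listed palbociclib risk. GGT increase appears only among events with insufficient evidence of a causal link, so the GGT half of the point is weaker. A reader might take the AST band of up to 20% as a rate for this DLT. It is a frequency band for the adverse-event term, with no grade or duration attached, and does not support that.

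**Other safeguards exist.** Weekly review of DLT evaluations (14.2.2) and the Day 42 recheck help once a value has been recorded. They do not help when none has.

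**Conclusion.** The inconsistency is established on the text: two of the three enzymes named in the liver-enzyme DLT clause are not required at any time point. Ascertainment of an AST- or GGT-only DLT is therefore left to local practice, and any error makes the dose look safer.

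The effect is modest and its size uncertain. The 4 to 12 point understatement of P(2 or more DLTs in 6) rests on three assumptions: a 2-5% rate of such DLTs, 10-25% from other causes, and no local testing. The documents supply none of these.

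A reader might go further and quote the chance that at least one such event arises in six patients, 1 − 0.98^6 = 11% to 1 − 0.95^6 = 26%, as the chance of a wrong dose decision. That does not follow. The decision changes only when a missed event moves the count across the two-DLT line. Nor do the documents support saying that liver toxicity in general goes unseen, since ALT and bilirubin are checked weekly in every patient. The point deserves correction because the remedy is cheap, not because the MTD is likely to be wrong.

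**What to change.** Add AST and GGT to the chemistry row in Section 8.1 (pre-study, weekly and Day 32) and to item j of the therapy delivery maps in Appendices VI and VII. Every patient then has a baseline and a series for each enzyme in the DLT clause, and the Day 42 recheck applies to any abnormal result. The cost is two analytes on blood already drawn and some extra abnormal values to record, with no added visit or procedure.

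If the sponsor does not want the extra tests, Section 5.4.1.1 and Appendix XI must be reconciled with Section 8.1 and both maps, stating explicitly how AST and GGT are treated for DLT. Deleting the two names from the exclusion bullet would not do this. They would then fall under the general Grade 3 or greater rule, so that even a rise that resolved in time could count, while testing remained optional. Section 6.1.1 ties the holding of palbociclib to a DLT under 5.4.1, so that deletion would also change when the drug is held. Which enzymes should count is for the sponsor to decide; the sections need to agree.

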8.2 Pharmacology (required)

8.2.1 Description of Studies and Assay

Palbociclib PK studies will be determined by a validated LC-MS/MS method.

8.2.2 Sampling Schedule (See Appendix VIII)

Plasma samples will be obtained at the following time points:

- **Day 1 of Cycle 1:** pre-dose, and at 1, 2, 4, 8 and 24 hours post-dose of palbociclib.
- **Day 11 of Cycle 1:** pre-dose, and at 1, 2 and 4, 8 and 24 hours post-dose of palbociclib.

8.2.3 Sample Collection and Handling Instructions

Blood samples (3-4 mL) to provide a minimum of 1.0 mL of plasma for PK analysis of palbociclib will be collected in tubes containing dipotassium ethylenediaminetetraacetic acid (K_2EDTA). Record the exact time that the sample is drawn along with the exact time that the drug is administered.

8.2.4 Sample Processing

Upon collection of the blood PK samples, keep the samples on wet ice at all times prior to processing to plasma.

- The blood samples have to be processed to plasma and placed in a freezer at -20°C within 1 hour of collection.

- To process the blood samples to plasma, centrifuge the blood samples in a refrigerated centrifuge at approximately 4 °C at about 1700 x g for approximately 10 minutes.
- Using a clean separate pipette for each time point, transfer the plasma samples into pre-labeled 4 or 5 mL polypropylene cryovials and store in the freezer at approximately -20°C until shipment. If a -20°C freezer is not available at the site the samples may be stored at -80°C. Palbociclib is stable at -20°C and -80°C for 439 days in frozen K2EDTA plasma.
- Ship the frozen samples on dry ice to the contract bioanalytical laboratory.

8.2.5 Sample Labeling

Each tube must be labeled with the patient's study registration number, the study I.D., and the date and time the sample was drawn. Data should be recorded on the Pharmacokinetic Study Form ([Appendix VIII](#)), which must accompany the sample(s).

8.2.6 Sample Shipping Instructions

A phone call or fax communication should precede all sample shipments. A phone or fax communication must precede all HIV positive or other known infectious sample shipments.

Detailed sample inventory information ([Appendix VIII](#)) must accompany the samples. Lack of paperwork or illegible information will delay sample login and analysis. Samples that are unclearly or incompletely labeled may also lead to delayed analysis.

Samples should be batched and shipped via overnight courier at the end of each cycle on Mondays, Tuesdays, or Wednesdays. Samples should be shipped to the following address:

8.3 **Correlative Biology Studies (Optional)**

8.3.1 Description of Studies

Correlative biology studies in bone marrow and peripheral blood will be performed in consenting patients to determine the biological activity of CDK4/6 inhibition. RNA sequencing and Western blotting will be used to determine gene and protein expression. Cell cycle analyses will be performed to determine the percentage of S phase cells prior to and after palbociclib exposure.

